9.2 Severity of Adverse Events

Each AE shall be assessed for its severity, by the Primary Investigator according to the criteria below.

Table 2: Severity of Adverse Event

Severity Rating	Description
Mild	Event, signs, or symptoms that do not interfere with the participant's daily activity, are usually considered self-limiting, can be treated with non-prescription type medications, and do not require medical intervention
Moderate	Event may interfere or cause low level inconvenience with the participant's daily activity. Requires medical intervention and/or treatment; however, unlikely to require hospitalization or be considered potentially life-threatening in nature
Severe	Event may cause significant discomfort to the participant and/or interferes with the participant's daily activity. Requires medical intervention and/or treatment to preclude a permanent impairment; may be life threatening and/or require hospitalization

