10.2 Sample Size Considerations

The primary objective of the study is to show the overall complication rate for Pristine is non-inferior to the performance goal at 3 months. If successful, the next step is to show superiority of Pristine at 3 months.

Based on hypothesis test of Non-inferiority

- Assumptions:
 - The complication rate of our performance goal is estimated at 31.5 events per 1000 patient days with a 90 days follow-up based on DOPPS study data. The complication rate for Pristine is expected to be similar.
 - The performance goal is set at 36.5 events per 1000 days using a 5 events per 1000 days non-inferiority margin;
 - The attrition through 90 days is assumed to be 15%
 - The Type 1 error is 0.025 (one-sided).

- The Type 2 error is 0.2.
- Sample Size:
 - Total required exposure is 12765 patient days which translates to 142 participants with average exposure of 90 days (PASS 2019).

Based on hypothesis test of Superiority

- Assumptions:
 - The complication rate of our performance goal is estimated at 31.5 events per 1000 patient days with a 90 days follow-up based on literature review, which is set as the performance goal.
 - The complication rate for the Pristine™ Catheter is assumed to be 26.5 events per 1000 patient days.
 - The attrition through 90 days is assumed to be 15%
 - The Type 1 error is 0.025 (one-sided).
- Sample Size:
 - Total exposure of 12765 patient days (which translates to 142 participants with average exposure of 90 days) will provide 85% power of the test (PASS 2019).

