Audit	Systematic examination of activities and documents related to a clinical investigation performed by (an) independent person(s) to determine whether these activities were conducted, and the data recorded, analyzed, and accurately reported, according to this CIP, standard operating procedures, applicable standards, and applicable regulatory requirements.
Audit trail	Documentation that allows reconstruction of the course of events.
(electronic) Case Report Forms (eCRFs)	Electronic documents for each participant on which information to be reported to the Sponsor is recorded, as required by this CIP.
Certified Copy / Printout	Copy (irrespective of the type of media used) of the original record that has been verified, (i.e. by a dated signature or by generation through a validated process), to have the same information including data that describe the context, content, and structure, as the original.
Chronic Kidney Disease	A term that includes stages such as mild, moderate, and severe loss of kidney function based on the patient's level of glomerular filtration rate (GFR).
Complications⁴	
Non-infectious complications are defined as:
 
Complication due to any noninfectious cause (thrombosis of the access, fibrin material within or around a catheter, catheter migration, central vein stenosis or thrombosis) requiring a revision procedure to maintain patency or improve access performance (i.e., thrombolysis, angioplasty, or surgical correction) in an inpatient or outpatient setting or removal or abandonment with creation of a new access that was not due to an access-related infection).³
 
Infectious Complications are defined as:
 
Complications due to any documented diagnosis of access infection requiring medical intervention (managed in an outpatient or inpatient setting) or sepsis as diagnosis in the hospitalization file whether access related or not.³

Term	Definition
Definitely Related AE	An AE is definitely related if it is obvious, certain or there is little doubt regarding the relationship.
Deviation	Instance(s) of failure to follow, intentionally or unintentionally, the requirements of this CIP.

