#### Infectious Complications

Complications due to any documented diagnosis of access infection requiring medical intervention (managed in an outpatient or inpatient setting) or sepsis as diagnosis in the hospitalization file whether access related or not.

Subject will be considered as having an infectious complication and will be counted as an event if the subject has experienced a device-related infection prior to the subject's end day of investigation period:

- **AE CRF Page:** Start Date of AE ≤ End Day of Investigation period **AND** Relationship to study Device: Equals 'Related' or 'Likely Related' **AND** Was event infectious: Equals Yes; subject will be considered as a failure at AE start date

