#### Non-infectious complications

Complication due to any noninfectious cause (thrombosis of the access, fibrin material within or around a catheter, catheter migration, central vein stenosis or thrombosis) requiring a revision procedure to maintain patency or improve access performance (i.e., thrombolysis, angioplasty, or surgical correction) in an inpatient or outpatient setting or removal or abandonment with creation of a new access that was not due to an access-related infection.

Subject will be considered as having a non-infectious complication and will be counted as an event if the subject has experienced a device-related non-infectious AE resulting in a re-intervention prior to the subject's end day of investigation period:

- **AE CRF Page:** Start Date of AE  $\leq$  End Day of Investigation period **AND** Relationship to study Device: Equals 'Related' or 'Likely Related' **AND** Was event infectious: Equals No **AND** Did AE Result in a Catheter Re-Intervention: Equals Yes; subject will be considered as a failure at AE start date

For each subject, the number of complications through the investigational duration is estimated as:

$$((\text{Number of observed infectious complications} + \text{Number of observed non-infectious complications}) * 1000) / \text{Length of investigation duration (Days)}$$

Length of investigation duration (Days) is from the date of index procedure to the end day of each subject's investigation period (End day of investigation period – Date of index procedure + 1); the end day of investigational period will be the earliest occurrence date of the following three events:

- If a subject's Pristine™ Catheter is removed due to Kidney Transplant, Transferred to AVG/AVF, Peritoneal Dialysis, Withdrawal of Care, or Other reasons, then the date of removal will be used to calculate the length of investigation duration. That is:
  - **Hemodialysis Catheter Re-Interventions CRF page:** Catheter removal Equals Yes **AND** Reason for catheter removal Equals: Kidney Transplant, Transferred to AVG/AVF, Peritoneal Dialysis, Withdrawal of Care, or Other; date of re-intervention is used in the estimation of investigation duration

$$\text{Length of investigation duration (Days)} = \text{Removal date} - \text{date of index procedure} + 1$$

- If a subject discontinues early, then the discontinuation date will be used to calculate the length of investigation duration.
 

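### The infectious counting rule in SAP 5.2.1 implements neither limb of the endpoint definition: it has no medical-intervention condition, and it drops sepsis not related to the device.

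*Protocol*

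**What the plan says.** The infectious definition is the same in Protocol 3.1, 4.2 and Appendix A and in SAP 2.7.1 and 5.2.1. One limb is "Complications due to any documented diagnosis of access infection requiring medical intervention (managed in an outpatient or inpatient setting"). The other is "sepsis as diagnosis in the hospitalization file whether access related or not".

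Directly below that definition, SAP 5.2.1 says how an event is found in the data. A subject "will be counted as an event if the subject has experienced a device-related infection prior to the subject's end day of investigation period". In CRF terms there are three conditions: the event starts on or before the end of the investigation period; the relationship to the device is rated related or likely related; and "Was event infectious: Equals Yes; subject will be considered as a failure at AE start date". No condition asks whether the infection was treated, and none lets in sepsis that is unrelated to the device.

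The companion rule for non-infectious complications does carry its own threshold: "Did AE Result in a Catheter Re-Intervention: Equals Yes; subject will be considered as a failure at AE start date".

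Protocol 9.2, Table 2, allows for events below the intervention threshold. Mild events are those that "can be treated with non-prescription type medications, and do not require medical intervention".

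Protocol 10.2 gives the benchmark rate: "The complication rate of our performance goal is estimated at 31.5 events per 1000 patient days with a 90 days follow-up based on DOPPS study". On the goal used for the non-inferiority test, the same section states: "The performance goal is set at 36.5 events per 1000 days using a 5 events per 1000 days non-inferiority margin".

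**The concern.** A single-arm test against a fixed goal is fair only if events are counted as they were for the goal. The protocol says the endpoint is derived from DOPPS, and Protocol 4.2 gives that study's clear complication definitions as one reason for choosing it. Yet the operational rule departs from the written definition in two ways.

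- It is too broad on intervention. A mild device-related exit-site infection that needed no medical intervention lies outside the definition but is counted.
- It is too narrow on relatedness. Sepsis in the hospital file counts under the definition even when it is not access related. The rule counts it only if the investigator links it to the device. Access infections rated unlikely or not related are lost in the same way.

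The first departure makes success harder to show and the second makes it easier. Either way, the infectious component would be reported under a definition it does not follow, in results that Protocol section 3 intends for labeling.

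**Working it through.** **Definition against rule**

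| Event | Written definition | SAP 5.2.1 rule |
|---|---|---|
| Device-related access infection, medical intervention needed | counted | counted |
| Device-related access infection, no medical intervention | not counted | counted |
| Access infection treated, but rated unlikely or not related to the device | counted | not counted |
| Hospital-file sepsis, unlikely or not related to the device | counted | not counted |

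The rule adds events in row 2 and removes events in rows 3 and 4.

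**Inputs** (Protocol 10.2, repeated in SAP 2.4): expected rate 31.5 and goal 36.5 per 1000 days for non-inferiority; 26.5 against 31.5 for superiority; one-sided alpha 0.025; type 2 error 0.2; attrition 15%; total exposure 12,765 days; 142 participants at 90 days.

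**Reproducing the plan**

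Evaluable exposure is 0.85 × 12,765 = 10,850 days. Under the goal the mean count is 0.0365 × 10,850 = 396.0. The largest count c with P(X ≤ c) ≤ 0.025 is 357 (actual alpha 0.02497). At 31.5 the mean is 341.8, and P(X ≤ 357) = 80.3%. The same steps for superiority give a critical count of 305 and power of 85.5%. The stated 80% and 85% both reproduce, so 12,765 days already includes the attrition allowance. Treating all 12,765 days as evaluable would give 85.7% and 90.5%, which are not the plan's figures.

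**Effect of a net change in the counted rate**

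The documents give no rate for untreated infections or for sepsis unrelated to the device. So x below is an assumed net change per 1000 days between the rule and the definition. Power is P(X ≤ 357) at rate 31.5 + x. False success is P(X ≤ 357) at 36.5 + x, that is, when the rate under the written definition truly equals the goal.

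| x per 1000 days | Events in 10,850 days | Non-inferiority power | False success |
|---|---|---|---|
| +0.5 | +5.4 | 71.2% | 1.3% |
| +0.25 | +2.7 | 76.0% | 1.8% |
| 0 | 0 | 80.3% | 2.5% |
| −0.25 | −2.7 | 84.2% | 3.4% |
| −0.5 | −5.4 | 87.5% | 4.5% |
| −1 | −10.9 | 92.7% | 7.8% |

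**Scale of each error, illustration only**

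The feasibility study (Protocol 2.1) reported 6 device-related infections. If all 45 participants had 180 days, that is 6 / (45 × 180) × 1000 = 0.74 per 1000 days. If 10% to 30% of these needed no intervention (an assumption), the rule adds 0.07 to 0.22 per 1000 days, about 1 to 2 events. Taken alone, that puts power at about 79% to 76.5%.

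The same study reported 3 infections not related to the device: 3 / (45 × 180) × 1000 = 0.37 per 1000 days. It does not say whether any was sepsis, so on this basis the number dropped could lie anywhere from none to 0.37. The two ranges overlap, and the sign of the net cannot be read from them.

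**The case against.** A reader might infer that the missing intervention condition inflates the Pristine rate and costs the trial power. That holds only for this omission taken alone. The device filter in the same rule removes events, and nothing in the documents shows that the net is upward. Inferring the opposite, that the rule as a whole favours success, is equally unsupported.

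Three further arguments deserve weight.

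- Taken alone, the omission is conservative. It does not raise the type 1 error, and its cost is some power. This stands.
- The likely number of events is small and rests on assumptions. The feasibility report does not say how many infections went untreated, and with 9 deaths not everyone could have had 180 days. This also stands, so the power figures are a scale and not a forecast.
- The AE CRF and the derived data specification (SAP Appendix 2) are not shown, and the full definition sits just above the rule. An intervention field may exist and a careful programmer might use it. But the rule names its CRF fields one by one. Followed as written, it applies no such test, while the non-infectious rule does apply its own. That contrast suggests an oversight.

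**Conclusion.** The mismatch is certain from the text: in SAP 5.2.1 the definition and the rule disagree on both limbs. The direction and size of the net effect are not known.

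After attrition the design has almost no slack (80.3% against a planned 80%), so even a net excess of 0.07 per 1000 days takes non-inferiority power just below plan, and 0.25 takes it to 76.0%. A net shortfall of 0.25 to 1 per 1000 days would raise false success to between 3.4% and 7.8%. These figures assume a Poisson count, 10,850 evaluable days and the assumed values of x.

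The point should be corrected because the primary count must follow its own definition and the edit is short. A proven loss of power is not the reason.

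**What to change.** Rewrite the infectious rule in SAP 5.2.1, and the derived data specification, so that it matches both limbs at once. Count an event that starts within the period if it is either:

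- (a) an access infection with recorded medical intervention, taken from treatment or action-taken data; or
- (b) any sepsis diagnosis in the hospitalization file, regardless of device relationship.

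State which CRF fields identify an access infection; SAP 5.3.1 already refers to a type-of-infection item on the AE page. Use AE severity only as a fallback for intervention, and only after the two severity scales are reconciled. Table 2 ties Moderate to medical intervention or treatment, whereas Appendix A allows Moderate for interference with usual activity alone. Severity is also an investigator judgement in an unblinded study.

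Do not add the intervention condition by itself. That would lower the count while leaving the device filter on sepsis, which is the side that favours success.

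Report infectious events that meet neither limb in the adverse event tables, and show the primary count under the current SAP rule as a sensitivity analysis.

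The cost is a few lines of SAP and programming text, plus a check that the CRF records treatment and hospital sepsis diagnoses; the CRF is not in the documents, so this cannot be confirmed here. A few mild infections would leave the primary count, and some sepsis events unrelated to the device would enter it.

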3.1 Primary Endpoint

Primary Safety and Performance Endpoint

This study has a combined Safety and Performance endpoint derived from the Dialysis Outcomes and Practice Patterns Study (DOPPS) data. The combined Primary Endpoint will be overall complications including infectious and non-infectious complications at 3 months.

Infectious Complications are defined as:

Complications due to any documented diagnosis of access infection requiring medical intervention (managed in an outpatient or inpatient setting) or sepsis as diagnosis in the hospitalization file whether access related or not.⁴

Non-infectious complications are defined as:

Complication due to any noninfectious cause (thrombosis of the access, fibrin material within or around a catheter, catheter migration, central vein stenosis or thrombosis) requiring a revision procedure to maintain patency or improve access performance (i.e., thrombolysis, angioplasty, or surgical correction) in an inpatient or outpatient setting or removal or abandonment with creation of a new access that was not due to an access-related infection).⁴

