Possibly Related AE	An AE is possibly related if it is capable of being related but relatively unlikely or there is insufficient information to determine if the AE is related to the device or procedure.
Post Procedure Event	AE that occurred after the index procedure.
Principal Investigator	Qualified person responsible for conducting the clinical investigation at an investigation site. If a clinical investigation is conducted by a team of individuals at an investigation site, the PI is responsible for leading the team.
Procedure access Site	A site of incision access during index procedure.
Procedural Event	AE that occurred during the index procedure.
Procedure Duration	The duration of the index procedure as defined in this CIP.
Procedure Related AE	AEs directly attributable to the index procedure.
Procedure Success	Successful catheter creation using the Pristine™ Long-Term Hemodialysis Catheter with flow confirmed through the catheter.
Recruitment	Active efforts to identify participants who can be suitable for enrolment into the clinical investigation.
Re-interventions	Any additional procedures with the initial catheter after the index procedure.
Screen Failure	A participant who is excluded from this clinical investigation as based on the eligibility criteria.
Serious Adverse Device Effect (SADE)	ADE that has resulted in any of the consequences characteristic of a SAE.

Term	Definition
Serious Adverse Event	
An AE that led to any of the following:
 
 • Death; or • Serious deterioration in the health of the participant, users or other persons as defined by one or more of the following: 
 - A life-threatening illness or injury; or - A permanent impairment of a body structure or a body function including chronic diseases; or - In-patient or prolonged existing hospitalization; or - Medical or surgical intervention to prevent life-threatening illness or injury or permanent impairment to a body structure or a body function; or • Fetal distress, fetal death or a congenital abnormality or birth defect including physical or mental impairment. 
Note: Planned hospital visits and / or hospital stays, or procedures required by this CIP (including subsequent interventions assessed in the clinical investigation endpoints), without serious deterioration in health should not be considered SAEs.

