Serious Health Threat	Signal from any AE or device deficiency that indicates an imminent risk of death or a serious deterioration in the health in participants, users, or other persons, and that requires prompt remedial action for other participants, users, or other persons. This would include events that are of significant and unexpected nature such that they become alarming as a potential serious health hazard or possibility of multiple deaths occurring at short intervals.
Severe AE	Symptom(s) causing severe discomfort to the participant and / or significant impact on the participant's usual activity. Additional intervention and / or treatment is necessary. Additional sequelae occur.
Severity (of AE)	The intensity of the AE as experienced by the participant or user.
Significant Deviation	A deviation that occurs to protect the life or physical well-being of a participant in an emergency, or a deviation that may affect the

Term	Definition
	scientific soundness of the clinical investigation, or a deviation pertaining to the rights, safety or welfare of human participants.
Source Data	All information in original records, certified copies of original records of clinical findings, observations, or other activities in a clinical investigation, necessary for the reconstruction and evaluation of the clinical investigation. This includes electronic source data initially recorded in an electronic format.
Source Document	Original or certified copy of printed, optical, or electronic document containing source data.
Sub-Investigator	Individual member of the investigation site team designated and supervised by the PI at an investigation site to perform clinical investigation-related procedures or to make important clinical investigation-related and medical treatment decisions.
Thrombosis	The formation or presence of a blood clot resulting in catheter occlusion.
Treated Participant	Defined as a participant that has met all eligibility criteria, into whom the Pristine™ Long-Term Hemodialysis Catheter was introduced and in whom procedure success was achieved.

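### SAP 5.2.1 counts non-infectious complications through a bare re-intervention flag, so the primary numerator can differ from the endpoint definition attached to the DOPPS-derived goal

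*Protocol*

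**What the plan says.** Protocol 3.1 (repeated in 4.2, Appendix A under Complications, and SAP 2.7.1 and 5.2.1) defines a non-infectious complication by cause and by what was done about it. The causes are access thrombosis, fibrin material in or around the catheter, catheter migration, and central vein stenosis or thrombosis. There are two routes to an event. One is a cause "requiring a revision procedure to maintain patency or improve access performance (i.e., thrombolysis, angioplasty, or surgical correction"). The other is "removal or abandonment with creation of a new access that was not due to an access-related infection". The protocol cites this definition to the DOPPS publication, and Protocol 4.2 gives the clarity of the DOPPS definitions as one reason for using DOPPS as the source of the goal.

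SAP 5.2.1 restates the definition and then gives the rule that produces the count. A subject has an event if the subject "has experienced a device-related non-infectious AE resulting in a re-intervention prior to the" end of the investigation period. On the AE page this means a start date within the period, "Relationship to study Device: Equals 'Related' or 'Likely Related"', not infectious, and "Did AE Result in a Catheter Re-Intervention: Equals Yes; subject will be considered as a failure at AE start date".

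Protocol Appendix A defines re-interventions as "Any additional procedures with the initial catheter after the index procedure". Neither document has another glossary entry for the term. The SAP does not define the CRF field and does not cite Appendix A for it.

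**The concern.** The endpoint asks why the procedure was done, or whether the access was lost and replaced. The rule asks only whether there was a catheter re-intervention. None of the cause list, the purpose and the new-access condition is carried into the fields that make the count.

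If sites answer the flag by the Appendix A wording, it can go wrong in both directions. It can miss a revision of the central vein with the catheter left in place, or abandonment without any procedure on the catheter. It can also take in a catheter procedure that follows a device-related, non-infectious adverse event but was not done for patency or performance.

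The single-arm comparison depends on counting events in the way the reference rate counted them. A net under-count makes it easier to pass a device whose true rate is at the goal. A net over-count costs power. The documents describe no endpoint adjudication that would correct the site's answer. The Medical Monitor's role in Protocol 9.5.1 is adverse-event trends and safety signals.

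**Working it through.** **1. Definition and rule side by side**

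| Condition | Endpoint definition | SAP 5.2.1 rule |
|---|---|---|
| Cause | Listed non-infectious causes, including central vein stenosis or thrombosis | Any non-infectious adverse event |
| Procedure | Revision for patency or performance | Catheter re-intervention = Yes, no purpose stated |
| Loss of access | Removal or abandonment with a new access, not for access infection | Not named. Removal is recorded on the Re-Interventions CRF page, so it can fall under the term; abandonment without a procedure has no clear route |
| Relatedness | None | Related or Likely Related to the device |

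The first three rows are this point. The fourth is a separate departure in the same rule.

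**2. Inputs (Protocol 10.2, SAP 2.4)**

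Goal 36.5 per 1000 days; expected rate 31.5; one-sided alpha 0.025; Type 2 error 0.2; attrition 15%; stated exposure 12,765 days, or 142 participants at 90 days; stated superiority power 85% (31.5 against 26.5).

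**3. Reproducing the plan's figures**

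The exact one-sided Poisson test passes if the count is at most c, the largest k with P(X ≤ k | 0.0365 × T) < 0.025.

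- At T = 10,850 days the mean at the goal is 0.0365 × 10,850 = 396.0, c = 357, alpha is 0.0250 and power at 31.5 is 80.3%.
- Inflating for attrition: 10,850 / 0.85 = 12,765 days, and 12,765 / 90 = 141.8, rounded up to 142.
- Superiority power at 10,850 days is 85.5%.

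The stated figures therefore reproduce with 10,850 days as the exposure after attrition. If all 12,765 days were observed, the mean at the goal is 465.9, c = 423 (33.1 per 1000), alpha is 0.0234 and power at 31.5 is 85.7%. Both exposures are carried below.

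**4. Net under-count (share m is an assumption)**

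False-pass probability at a true 36.5 = P(X ≤ c | 0.0365 × T × (1 − m)).

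| Net share missed | 10,850 days: events missed, pass probability | 12,765 days: events missed, pass probability |
|---|---|---|
| 0 | 0, 2.5% | 0, 2.3% |
| 1% | 4.0, 3.9% | 4.7, 3.8% |
| 2% | 7.9, 5.9% | 9.3, 5.9% |
| 5% | 19.8, 16.7% | 23.3, 18.2% |

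**5. Net over-count (0.5 per 1000 days is an assumption)**

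Power at a true 31.5 = P(X ≤ c | 0.0320 × T).

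- 10,850 days: 0.0005 × 10,850 = 5.4 extra events; power falls from 80.3% to 71.2%.
- 12,765 days: 0.0005 × 12,765 = 6.4 extra events; power falls from 85.7% to 77.2%.

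**The case against.** The strongest reply is that the link from Appendix A to the CRF field is inferred. SAP 5.2.1 does not cite the glossary, it prints the full endpoint definition directly above the rule, and neither the CRF nor the derived data specification (SAP Appendix 2) is available here. A site might answer the flag with the endpoint in mind. This stands, and it limits the point to what the numerator can do. It does not remove the inconsistency, because the rule as written contains none of the definition's conditions and no other glossary definition fills the gap.

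A reader might go further and infer the following. The documents do not support these readings.

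- **Central-vein angioplasty is certainly excluded.** The glossary phrase can also mean procedures while the first catheter is in use, as opposed to a replacement. Protocol 7.3 describes re-interventions up to discharge with no catheter limit, while Protocol 7.4.1 speaks of catheter re-interventions during follow-up. The term is loose rather than settled.
- **Every catheter procedure is counted.** The procedure must result from a non-infectious adverse event rated Related or Likely Related. An elective removal for transfer to AVF or AVG without such an event ends exposure and adds nothing to the count. Any remaining over-count works against the device.
- **The glossary entry for Thrombosis ("The formation or presence of a blood clot resulting in catheter occlusion") narrows the primary count.** The rule has no thrombosis field, so changing that entry would alter no count under it.
- **A 10% loss is a fair scenario.** It gives a false-pass rate of 53-58%, but it means about 40 to 47 missed events in three months among 142 participants, in a trial that excludes known central venous stenosis. Infectious events are not affected by the flag, so the missed share of non-infectious events would be larger still. Nothing in the documents supports that figure, and 5% is already at the high end.

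**Conclusion.** The point holds in a limited form. The SAP's counting rule for non-infectious complications is not the endpoint definition cited to DOPPS, and the only glossary meaning of its key term has no purpose condition and is tied to the catheter. The primary numerator can therefore differ from the definition attached to the goal. That it will differ, by how much and in which net direction cannot be established from the documents.

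The calculation shows sensitivity, not an estimate of bias. Small net misses of 1-2% move the false-pass rate to about 4-6%, and 5% moves it to 17-18%. An over-count of 0.5 per 1000 days costs about nine percentage points of power. These figures assume the exact Poisson test and the plan's own rates and exposure.

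The relatedness filter in the same rule is a separate departure. It is absent from the endpoint definition and can only lower the count. In the parallel infectious rule it conflicts with "sepsis as diagnosis in the hospitalization file whether access related or not". Correcting the re-intervention term alone would leave the numerator mismatched. The point merits correction before analysis.

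**What to change.** - In SAP 5.2.1 and the CRF completion instruction, define the flag for the primary endpoint in the endpoint's existing words: a listed cause "requiring a revision procedure to maintain patency or improve access performance (i.e., thrombolysis, angioplasty, or surgical correction"), stating that this includes central vein stenosis or thrombosis, or "removal or abandonment with creation of a new access that was not due to an access-related infection".
- Align the Appendix A entry for re-interventions with that wording, or state that the general entry does not govern the primary endpoint.
- List other catheter procedures separately, outside the primary count.
- Reconcile the Related/Likely Related filter with the endpoint definition, or justify it. If it stays, add a sensitivity count under the full definition.

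The cost is wording in the SAP and Appendix A and one CRF instruction, with no extra visits or participants. Adverse events already entered may need their flag checked against the clarified wording. The observed rate may move slightly in either direction.
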